APPENDIX 6: IOP MEASUREMENT

IOP measurements will be performed utilizing Goldmann applanation tonometry according to the Investigator's standard procedure. All pressures will be recorded in mmHg.

APPENDIX 7: DILATED OPHTHALMOSCOPY

Dilated Ophthalmoscopy will include assessment of the optic nerve head for pallor and cupping (cup to disc ratio). After the Ophthalmoscopy procedure, the Investigator will determine if findings are within normal limits or are abnormal. For abnormal findings at Visit 1, the Investigator will determine whether or not the abnormality would exclude subject from study participation.

APPENDIX 8: EYE DISCOMFORT, EYE DRYNESS SYMPTOM ASSESSMENT

Symptom Assessment Visual Analog Scale (VAS)

Subjects will be asked the following questions regarding their current symptoms (unrelated to IP instillation) at each visit.

The subject will be asked to subjectively rate each ocular symptom (OU) by placing a vertical mark on the horizontal line to indicate the level of eye discomfort and dryness. 0 corresponds to “No Symptoms” and 100 corresponds to “Severe Symptoms”

[figure not shown]
Subject Instructions: Please review the symptoms below. After your review, please rate how your eyes feel using 1 score for both eyes for each of the following symptoms by placing a single vertical mark that represents how your symptom feels at this moment.

0 = No Symptoms and 100 = Severe Symptoms

Eye Discomfort	0	100
<hr/>		
Eye Dryness	0	100
<hr/>		

APPENDIX 9: CORNEAL FLUORESCEIN STAINING (CFS) / NATIONAL EYE INSTITUTE / INDUSTRY WORKSHOP SCALE

The 5 areas of the cornea will be scored by the Investigator according to the following scoring system and the total score will also be calculated. Details regarding the procedure will be provided in the Manual of Procedures.

Score each of the five regions of each eye using the modified grading scale of 0–4 with 0.5 grade increments and the description provided.

None	0 = no staining
Trace	1 = few/rare punctate lesions
Mild	2 = discrete and countable lesions
Moderate	3 = lesions too numerous to count but not coalescent
Severe	4 = coalescent

Reference: modified from [Lemp \(1995\)](#) and [Shimmura \(1995\)](#)

APPENDIX 10: UNANESTHETIZED SCHIRMER TEST

The Schirmer test will be conducted on unanesthetized eyes. A 35 mm x 5 mm filter paper strip is used to measure the amount of tears that are produced over 5 minutes. The strip is placed in the lower eyelid margin of both eyes without the use of a preplaced ophthalmic anesthetic drop. After 5 minutes, the strip is removed and the amount of wetting is measured in millimeters.

APPENDIX 11: SANDE

PLEASE COMPLETE THE FOLLOWING QUESTIONS REGARDING THE FREQUENCY AND SEVERITY OF YOUR DRY EYE SYMPTOMS.

1. Frequency of symptoms:

Please place an 'X' on the line to indicate how often, on average, your eyes feel **dry and/or irritated**:

Rarely _____ All the time

2. Severity of symptoms:

Please place an 'X' on the line to indicate how severe, on average, you feel your symptoms of dryness and/or irritation are:

Very Mild _____ Very Severe

Appendix 12: Daily Dosing Diary

Subjects will be asked to record each day the following information related to administration of IP:

- Date
- Time
- Yes/No for administration of each dose

IP	Investigational Product
LogMAR	Logarithm of the Minimum Angle of Resolution
MedDRA	Medical Dictionary for Regulatory Activities
NEI	National Eye Institute
OD	Oculus Dextrus (right eye)
OU	Oculus Uterque (both eyes)
P	Probability
PPS	Per Protocol Set
SAE	Serious Adverse Event
SAF	Safety Set
SANDE	Symptom Assessment Questionnaire iN Dry Eye
SAP	Statistical analysis plan
TEAE	Treatment-Emergent Adverse Events

Statistical Analysis Plan

Sponsor:	VivaVision Biotech, Inc.		
Protocol:	VVN001-CS-201		
Document Version No.:	V3.0	Document Date:	13-JAN-2022

Abbreviation

tCFS Total Corneal Fluorescein Staining

VA Visual Acuity

VAS Visual Analog Scale

Definition

Statistical Analysis Plan

Sponsor:	VivaVision Biotech, Inc.		
Protocol:	VVN001-CS-201		
Document Version No.:	V3.0	Document Date:	13-JAN-2022

1. INTRODUCTION AND OBJECTIVES OF ANALYSIS

1.1. Introduction

This document presents the statistical analysis plan (SAP) for VivaVision Biotech, Inc., Protocol VVN001-CS-201: “A Phase 2a, Double-Masked, Randomized, Vehicle-controlled Trial Evaluating the Safety and Efficacy Activity of 1% and 5% VVN001 compared to Vehicle in Subjects with Dry Eye Disease”.

The SAP is based on the final protocol dated June 17,2020 and the purpose of this document is to outline the appropriate statistical approaches to be used in the analysis of study data in order to answer the study objectives. The populations for analysis defined, data handling rules, statistical methods, and formats for data presentation are provided. The statistical analyses and summary tabulations described in this SAP will also provide the basis for the results sections of the clinical study report (CSR) for this trial.

This SAP also will outline any differences in the currently planned analytical objectives relative to those planned in the study protocol.

1.2. Objectives of Statistical Analysis

1.2.1. Primary Objective

The primary objective of this trial is to evaluate the safety and tolerability of VVN001, 1% ophthalmic solution and VVN001, 5% ophthalmic solution when administered BID compared to vehicle administered BID.

1.2.2. Secondary Objective

The secondary objective is to evaluate the efficacy activity of VVN001, 1% ophthalmic solution and VVN001, 5% ophthalmic solution administered BID compared to vehicle administered BID in the treatment of signs and symptoms of DED.

Sponsor:	VivaVision Biotech, Inc.		
Protocol:	VVN001-CS-201		
Document Version No.:	V3.0	Document Date:	13-JAN-2022

2. STUDY DESIGN

[figure not shown]
2.1. Synopsis of Study Design

This is a Phase 2a, multi-center, double-masked, randomized, vehicle-controlled, parallel-group study designed to evaluate the safety and tolerability and to explore the efficacy activity of VVN001 1% and 5% Ophthalmic solution versus vehicle in subjects with dry eye disease. Approximately 165 subjects who meet inclusion/exclusion criteria will be eligible for randomization in 1:1:1 ratio to one of the 3 treatment groups: VVN001 Ophthalmic solution 1%, 5% or vehicle.

The study will consist of two periods over 14-weeks total: screening/run-in period (Day -14 to Day -1), and treatment period (Day 1 to Day 84).

2.1.1. Study Schematic

Figure 1. Study Visits Schematic

Statistical Analysis Plan

Sponsor:	VivaVision Biotech, Inc.		
Protocol:	VVN001-CS-201		
Document Version No.:	V3.0	Document Date:	13-JAN-2022

2.1.2. Study Eye

Subjects must replicate the following findings in the same eye at Visits 1 and 2 in order to be considered for further study eligibility: 1) Inferior CFS score ≥ 2 (0 - 4 scale) and 2) Schirmer score STT without anesthesia ≥ 1 and ≤ 7 mm, at Visit 1 and 2. If both eyes meet the two criteria above, the eye with the greater inferior CFS at Visit 2 will be selected as the study eye. If both eyes have an equal inferior CFS score at Visit 2, the eye with the lowest STT value at Visit 2 will be designated as the study eye. If both eyes have equal score in inferior CFS scores and equal STT values at Visit 2, the right eye (OD) will be selected as the study eye.

2.1.3. Study Treatment

VVN001 Ophthalmic Solution 1%, 5% or Vehicle will be administered to the ocular surface twice daily as a single drop in each eye administered morning and evening. The first dose of Single-Masked Vehicle and the first dose of Double-Masked IP (VVN001 1%, 5% or Vehicle) will be self-administered in the morning dose for that day. Following Visit 1, the second dose of Single-Masked IP will be received in the evening for approximately 14 days. Following Visit 2, the subject will be instructed to self-administer the second dose of Double-Masked IP in the evening BID instilled into each eye bilaterally for approximately 84 days.

2.2. Randomization Methodology

Approximately 165 subjects will be randomized by permuted block in this study at approximately 10 centers located in the United States. Subjects will be randomized to one of the following 3 treatment groups VVN001 1%, 5% or Vehicle in a 1:1:1 ratio.

2.3. Study Procedures

The schedule of assessments, as outlined in the study protocol, is provided in Table 1.

Statistical Analysis Plan

Sponsor:	VivaVision Biotech, Inc.				
Protocol:	VVN001-CS-201				
Document Version No.:	V3.0	Document Date:		13-JAN-2022	

Table 1 Schedule of Assessments

	VISIT 1	VISIT 2	VISIT 3	VISIT 4	VISIT 5	VISIT 6
	SCREENING	RANDOMIZATION	TREATMENT VISIT	TREATMENT VISIT	TREATMENT VISIT	FINAL TREATMENT VISIT
	DAY -14 (+/-1 DAY)	DAY 1 (+/-2 DAYS)	DAY 14 (+/-2 DAYS)	DAY 28 (+/-2 DAYS)	DAY 56 (+/-2 DAYS)	DAY 84 (+/-2 DAYS)
INFORMED CONSENT AND MEDICAL HISTORY	X					
INCLUSION/EXCLUSION CRITERIA ^a	X	X				
CONCOMITANT MEDICATION QUERY	X	X	X	X	X	X
ASSESS PRIOR ARTIFICIAL TEAR USE	X					
CLINICAL SAFETY LABORATORIES AND HEMATOLOGY	X					X
ADVERSE EVENT QUERY		X	X	X	X	X
COLLECT STUDY DRUG		X _b		X _c	X _c	X _c
SUBJECT-REPORTED 2-SYMPTOM ASSESSMENT (EYE DRYNESS AND EYE DISCOMFORT; VAS)	X	X	X	X	X	X
SANDE	X	X	X	X	X	X
PREGNANCY TEST ^a	X					X
BCVA	X	X	X	X	X	X
	VISIT 1	VISIT 2	VISIT 3	VISIT 4	VISIT 5	VISIT 6
	SCREENING	RANDOMIZATION	TREATMENT VISIT	TREATMENT VISIT	TREATMENT VISIT	FINAL TREATMENT VISIT

Statistical Analysis Plan

Sponsor:	VivaVision Biotech, Inc.				
Protocol:	VVN001-CS-201				
Document Version No.:	V3.0	Document Date:		13-JAN-2022	

	DAY - 14 (+/-1 DAY)	DAY 1 (+/-2 DAYS)	DAY 14 (+/-2 DAYS)	DAY 28 (+/-2 DAYS)	DAY 56 (+/-2 DAYS)	DAY 84 (+/-2 DAYS)
BIOMICROSCOPY/EXTERNAL EYE EXAM	X	X	X	X	X	X
CFS STAINING	X	X	X	X	X	X
SCHIRMER (WITHOUT ANESTHESIA)	X	X	X	X	X	X
IOP	X	X	X	X	X	X
DILATED OPHTHALMOSCOPY	X					X
IP ADMINISTRATION IN CLINIC	X _b	X _c				X _c
DROP COMFORT ASSESSMENT	X	X				X
DISPENSE IP	X _b	X _c		X _c	X _c	
DISPENSE DOSING AND SYMPTOM DIARY (AS NEEDED)	X	X		X	X	
COLLECT DAILY DIARY		X	X	X	X	X
EXIT STUDY						X

^aWomen of childbearing potential only; ^bRun-In Drug; ^cDouble-Masked IP;
dSubjects must replicate the following findings in the same eye at Visits 1 and 2 in order to be considered for further study eligibility: 1) Inferior CFS score ≥ 2 (0 – 4 scale; using 0.5 increments) and (2) STT without anesthesia ≥ 1 and ≤ 7 mm, at Visits 1 and 2. If both eyes meet the two criteria above, the eye with the greater inferior CFS be selected as the study eye. If both eyes have an equal inferior CFS score at Visit 2, the eye with the lowest STT value at Visit 2 will be designated as the study eye. If both eyes have equal score in inferior CFS and equal STT scores at Visit 2, the right eye (OD) will be selected as the study eye.

Sponsor:	VivaVision Biotech, Inc.		
Protocol:	VVN001-CS-201		
Document Version No.:	V3.0	Document Date:	13-JAN-2022

2.4. Safety and Efficacy Variables

2.4.1. Safety Variables

The safety variables including OU are as follows:

- Ocular and non-ocular adverse events
- Slit-lamp Biomicroscopy and external eye exam
- Conjunctival hyperemia score
- Intraocular Pressure (IOP) measurement
- Dilated Ophthalmoscopy
- Best Corrected Visual Acuity (BCVA)
- Drop Comfort/Tolerability Assessment

2.4.2. Efficacy Variables

2.4.2.1. Primary Efficacy Endpoint

Mean Change from baseline (Visit 2) to Day 84 (Visit 6) in inferior region of CFS (iCFS) using the modified NEI/Industry Workshop (0-4 scale, using 0.5-unit increments)

2.4.2.2. Secondary Efficacy Endpoints

The secondary endpoints will be evaluated in a hierarchical fashion and tested sequentially starting with the key secondary endpoint below:

- **Key Secondary Endpoint:**

Mean change from baseline (Visit 2) to Day 84 (Visit 6) in the individual symptom of eye dryness (0 -100 VAS scale)

- **Other Secondary Endpoints:**

1. Mean Change from baseline (Visit 2) to Days 14 (Visit 3), 28 (Visit 4), 56 (Visit 5) and 84 (Visit 6) in total CFS (**tCFS**) using the modified NEI/Industry Workshop (0-20 scale; using 0.5-unit increments)
2. Mean Change from baseline (Visit 2) to Days 14 (Visit 3), 28 (Visit 4), Day 56 (Visit 5) and Day 84 (Visit 6) in each **individual subregion** (inferior (except for Day 84), nasal, temporal, central and superior) of CFS using modified NEI/Industry Workshop (0-4 scale; using 0.5 unit increments)

Statistical Analysis Plan

Sponsor:	VivaVision Biotech, Inc.		
Protocol:	VVN001-CS-201		
Document Version No.:	V3.0	Document Date:	13-JAN-2022

3. Mean Change from baseline (Visit 2) to Days 14 (Visit 3), 28 (Visit 4) and 56 (Visit 5) in the individual symptom of eye dryness (0-100 VAS scale)
4. Mean Change from baseline (Visit 2) to Days 14 (Visit 3), 28 (Visit 4) 56 (Visit 5) and 84 (Visit 6) in the individual symptom of eye discomfort (0-100 VAS scale)
5. Mean Change from baseline (Visit 2) to Days 14 (Visit 3), 28 (Visit 4), 56 (Visit 5) and Day 84 (Visit 6) in SANDE.
6. Mean Change from baseline (Visit 2) to Days 14 (Visit 3), 28 (Visit 4), 56 (Visit 5) and Day 84 (Visit 6) in Schirmer

Statistical Analysis Plan

Sponsor:	VivaVision Biotech, Inc.		
Protocol:	VVN001-CS-201		
Document Version No.:	V3.0	Document Date:	13-JAN-2022

3. SUBJECT POPULATIONS

3.1. Population Definitions

The following subject populations will be evaluated and used for presentation and analysis of the data:

- **Full Analysis Set (FAS)** - includes all randomized subjects who have received at least one dose of the IP. The efficacy and baseline analysis will be performed on the FAS. Subjects in the FAS will be analyzed as randomized.
- **Per Protocol Set (PPS)** - includes subjects in the FAS who do not have protocol deviations that impact the primary efficacy variable, and who complete the study. The PPS will be analyzed using observed data only for efficacy variables. Subjects in the PPS will be analyzed as treated. Sensitivity analyses may be performed on the PPS.
- **Safety Set (SAF)** - includes all randomized subjects who have received at least one dose of the IP. The SAF will be analyzed for all safety assessments. Subjects in the SAF will be analyzed as treated.

3.2. Protocol Deviations

At the discretion of the sponsor, major protocol deviations as determined by a review of the data prior to unmasking of the study results and the conduct of statistical analyses may result in the removal of a subject's data from the PPS. This file will include a description of the protocol deviations, and clearly identify whether this deviation warrants exclusion from the PPS. It will be finalized prior to hard database lock and unmasking. All protocol deviations will be captured in the CRF and summarized by treatment group and overall. The data listing for the protocol deviations will be also presented.

Sponsor:	VivaVision Biotech, Inc.		
Protocol:	VVN001-CS-201		
Document Version No.:	V3.0	Document Date:	13-JAN-2022

4. STATISTICAL METHODS

4.1. Sample Size Justification

A sample size of 55 subjects per treatment group will have 80% power to detect a treatment difference of 0.43 units with a common standard deviation 0.80 in iCFS score, and a treatment difference of 13.75 units with a common standard deviation 25.5 in eye dryness score at Visit 6/Day 84 using a t-test with a 0.05 two-sided significance level.

4.2. General Statistical Methods and Data Handling

4.2.1. General Methods

All output will be incorporated into Microsoft Excel or Word files, sorted and labeled according to the International Conference on Harmonisation (ICH) recommendations, and formatted to the appropriate page size(s).

Tabulations will be produced for appropriate demographic, baseline, efficacy and safety parameters. For categorical variables, summary tabulations of the number and percentage within each category (with a category for missing data) of the parameter will be presented by treatment group and visit (as applicable). For continuous variables, the sample size (n), mean, median, standard deviation, minimum and maximum values will be summarized by treatment group and visit (as applicable). All study data will be listed by treatment group, subject and visit (as applicable).

Formal statistical hypothesis testing will be performed on the primary and secondary efficacy endpoints with all tests conducted at the 2-sided, 0.05 level of significance.

4.2.2. Computing Environment

All descriptive statistical analyses will be performed using SAS statistical software (Version 9.4, SAS/STAT 15.1), unless otherwise noted. Medical History and adverse events will be coding using MedDRA version 23.0. Concomitant medications will be coded using World Health Organization (WHO) Drug version B3 WHO Drug Global – Mar 2020.

4.2.3. Methods of Pooling Data

Not applicable to the present study.

Sponsor:	VivaVision Biotech, Inc.		
Protocol:	VVN001-CS-201		
Document Version No.:	V3.0	Document Date:	13-JAN-2022

4.2.4. Adjustments for Covariates

Analyses of the change from baseline in primary and secondary efficacy endpoints utilizing repeated measures mixed model will adjust for the baseline score of the parameter of interest as a continuous covariate, treatment group as the main effect, and visit as a repeated measure on subject in the model.

4.2.5. Multiple Comparisons/Multiplicity

To avoid inflation of the type I error rate due to multiple hypotheses, the analysis of primary and key secondary efficacy endpoints will be conducted in the following hierarchical tests:

- 1) Primary (iCFS on Day 84, study eye) high concentration vs. vehicle
- 2) Primary (iCFS on Day 84, study eye) low concentration vs. vehicle
- 3) Key secondary (Eye Dryness VAS on Day 84) high concentration vs. vehicle
- 4) Key secondary (Eye Dryness VAS on Day 84) low concentration vs. vehicle

The comparisons will be conducted by using the repeated measure mixed model at the 5% significance level. Each comparison will be made in order until 2- sided p value > 0.05 . If p value ≤ 0.05 , then comparison is statistically significant, and testing is continued.

If both primary and key secondary efficacy endpoints demonstrate statistically significant superiority of each concentration of VVN001 versus vehicle at the two-sided 5% level, the similar hierarchical tests defined above will be conducted for the other secondary efficacy endpoints in the order of Day 84, Day 56, Day 28, Day 14 and in the order of presentation high concentration, low concentration within each endpoint specified in Section 2.4.2.2.

4.2.6. Subpopulations

No analyses of subgroups of subjects are planned.

4.2.7. Withdrawals, Dropouts, Loss to Follow-up

Subjects who withdrew from the study were not to be replaced.

4.2.8. Missing, Unused, and Spurious Data

Any missing, unused, or spurious data will be noted in the final clinical study report. Missing data will be handled as follows. Missing data for other data points not covered below will be left as missing.

Sponsor:	VivaVision Biotech, Inc.		
Protocol:	VVN001-CS-201		
Document Version No.:	V3.0	Document Date:	13-JAN-2022

4.2.8.1. Imputation Method for Efficacy Endpoints

Sensitivity analyses specified in Section 4.7.1.1 for the primary endpoint on FAS population will be performed by imputing missing data in terms of using last observation carried forward (LOCF) as well as observed data only. Additional sensitivity analysis will be examined if needed.

4.2.8.2. Missing Dates

If the start date/time of an AE is partially or completely missing, the date/time will be compared as far as possible with the date/time of the start of administration of study drug. The AE will be assumed to be treatment-emergent if it cannot be definitively shown that the AE did not occur or worsen during the treatment-emergent period (worst case approach). Listings will display the available date data.

The following general rules will be used:

- If the start time of an AE is missing but the start date is complete, an AE will only be excluded as being treatment-emergent if the start date is before the date of study drug administration or if the stop date/time is before study drug administration.
- If the start time and day are missing but the start month and year are complete, an AE will only be excluded as being treatment-emergent if the start month/year is before the month/year of study drug administration or if the stop date/time is before study drug administration.
- If the start day and month are missing but the start year is complete, an AE will only be excluded as being treatment-emergent if start year is before the year of study drug administration or if the stop date/time is before study drug administration.
- If the start date is completely missing, an AE will be considered treatment-emergent unless the stop date/time is before study drug administration.

The above general rules are applicable to the partially or completely missing worsening date/time of AE as well.

4.2.9. Visit Windows

Visit windows will be calculated based on the schedule of assessments in Table 1. Any visits or procedures performed outside the scheduled visits must be documented in the Unscheduled Visit page of the eCRF. Although there is a visit window of ± 2 days around the expected visit date, nominal visits will be used for the per-visit analyses for all the endpoints. In addition, for primary and key secondary efficacy endpoints, the unscheduled visit or early termination visit

Statistical Analysis Plan

Sponsor:	VivaVision Biotech, Inc.		
Protocol:	VVN001-CS-201		
Document Version No.:	V3.0	Document Date:	13-JAN-2022

will be mapped to the scheduled visit which is closest to the midpoint of two consecutive visit windows.

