6.1.7. Early Termination Visit

In the event of termination prior to Visit 6, every attempt will be made to ensure that all the Visit 6 assessments are performed in both eyes at the Early Termination Visit prior to discharge from the study.

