4.8.1. Safety Assessments

The following safety assessments will be summarized at each visit if applicable using descriptive statistics for SAF population by treatment group and overall. Assessments will be presented for study eye and non-study eye separately.

- Slit-Lamp biomicroscopy and external eye exam
 - For each anterior segment such as lashes, eyelid, conjunctiva, cornea, anterior chamber, lens pathology and sclera, the summary tabulations of the frequency and percentage for evaluation category such as normal, abnormal CS (clinically significant) and abnormal NCS (non-clinically significant) will be presented. The worsening (from normal to abnormal CS\NCS) change from baseline will be flagged in the data listing.
- Dilated Ophthalmoscopy
 - The evaluation of normal and abnormal for each eye in retina and optic nerve exam will be tabulated by using the frequency and percentage. The cup-to-disc ratio by visits and absolute change from baseline at Visit 6 (Day 84) will be presented using descriptive statistics.
- Intraocular Pressure (IOP) measurement (mmHg)
 - Absolute change from baseline at post-baseline visits will be summarized using descriptive statistics. The frequency and percentage of subjects with increase in $IOP \geq 10$ mmHg from baseline at each post-baseline visits and any visit will be summarized and presented in the data listing as well.
- Best Corrected Visual Acuity (BCVA)
 - LogMAR Visual Acuity (VA) score and change from baseline will be calculated and summarized using descriptive statistics. The frequency and percentage of

Statistical Analysis Plan

Sponsor:	VivaVision Biotech, Inc.		
Protocol:	VVN001-CS-201		
Document Version No.:	V3.0	Document Date:	13-JAN-2022

subjects with loss in VA ≥ 0.3 LogMAR (3 lines) from baseline at each post-baseline visits and any visit will be summarized and presented in the data listing.

- Conjunctival Hyperemia Evaluation
 - Overall bulbar conjunctival hyperemia grading scale: none, very slightly, slight, moderate and severe will be tabulated by using the frequency and percentage for each eye. The worsening (from low to high grading scale) change from baseline will be flagged in the data listing.
- Drop Comfort/Tolerability Assessment
 - The one scored for both eyes on VAS range from 0 to 10 at 1-minute and 5-minute post dose and absolute change from baseline at Visit 6 (Day 84) will be summarized using descriptive statistics.

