4.8.3. Laboratory Data

Safety laboratory tests will be collected in the central laboratory at Visit 1 and Visit 6. The actual continuous value and change from Visit 1 to Visit 6 will be summarized for each clinical laboratory parameter, including hematology, clinical chemistry, and urinalysis . All laboratory data will be provided in data listings. Urine pregnancy test results will be captured at Visit 1 and Visit 6. Urine pregnancy test results will be provided in data listing.

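### Early-termination values of ophthalmoscopy, laboratory tests and drop comfort enter no planned by-arm change summary, because the SAP defines these changes only at Visit 6

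*SAP*

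**What the plan says.** **Collection.** For a subject who leaves before Visit 6, Protocol 6.1.7 says that "every attempt will be made to ensure that all the Visit 6 assessments are performed in both eyes at the Early Termination Visit". Protocol 5.1 makes a similar request for discontinued subjects. Protocol 6.1.8 allows ophthalmic assessments at unscheduled visits.

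**Schedule** (Protocol Appendix 1, SAP Table 1). Dilated ophthalmoscopy and safety laboratory tests are done at Visits 1 and 6. Drop comfort is rated at Visits 1, 2 and 6.

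**Visit assignment.** SAP 4.2.9 states that "nominal visits will be used for the per-visit analyses for all the endpoints". It then adds one exception, split over a page break: "In addition, for primary and key secondary efficacy endpoints, the unscheduled visit or early termination visit" / "will be mapped to the scheduled visit which is closest to the midpoint of two consecutive visit windows". No corresponding rule is given for safety data.

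**Summaries.** For ophthalmoscopy, SAP 4.8.1 says: "The cup-to-disc ratio by visits and absolute change from baseline at Visit 6 (Day 84) will be presented using descriptive statistics". The same section places drop-comfort change at Visit 6. For laboratory data, SAP 4.8.3 says: "The actual continuous value and change from Visit 1 to Visit 6 will be summarized for each clinical laboratory parameter". The titles of Tables 14.3.6.x, 14.3.11 and 14.3.13.x indicate by-visit layouts, and none names an ET or last-value row.

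**Missing data.** SAP 4.2.8 has rules for efficacy imputation and partial AE dates. Beyond those, "Missing data for other data points not covered below will be left as missing".

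**The concern.** SAP 1.2.1 makes safety and tolerability the primary objective. The plan recognises that ET and unscheduled data need an analysis rule, but writes one only for iCFS and eye dryness. For an early leaver, the ET examination and blood draw may be the only post-randomization ophthalmoscopy and laboratory values. If they are collected but left out of the summaries, the change tables describe subjects who reached Visit 6.

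Subjects may leave because of eye problems, so this selection may be related to what is being summarised. If withdrawal also differs between arms, the comparison of Visit 6 values could understate late findings in the arm that loses more subjects.

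**Working it through.** **The plan's own figure.** The only computed design figure is 55 per group. With n = 2(1.96 + 0.8416)² × SD² / difference²:
- iCFS: 2 × 7.849 × 0.80² / 0.43² = 54.3, so 55.
- Eye dryness: 2 × 7.849 × 25.5² / 13.75² = 53.99, so 54.

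The figure reproduces. It matters here only as the denominator: 3 × 55 = 165.

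**Step 1: follow a Day 30 leaver through the rules.** The ET visit is not a scheduled visit; SAP 4.2.9 names it separately. Nominal-visit analysis therefore leaves this subject's Visit 6 cell empty. The mapping exception covers only the two lead efficacy endpoints, and SAP 4.2.8 does not fill the cell. The change summaries for cup-to-disc ratio, comfort and laboratory values look only at Visit 6, so this subject contributes nothing to them, even with a complete ET visit.

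**Step 2: would extending the mapping help?** The target wording is not fully clear. Taking it as a cut at the midpoint between scheduled visits:
- Between Days 28 and 56 the cut is Day 42, so the Day 30 leaver goes to Visit 4. None of the three assessments is scheduled there.
- Between Days 56 and 84 the cut is (56 + 84)/2 = Day 70. Only exits from Day 70 onward reach Visit 6.
- If exits are assumed uniform over Days 1-84, that share is (84 − 70)/(84 − 1) = 14/83 = 17%.

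Extending the mapping would leave about 83% of leavers outside the Visit 6 summaries.

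**Step 3: how many subjects?** No dropout rate is given, so a range is assumed.

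| Assumed early termination | Leavers of 165 | Remaining per arm of 55 | Leavers reaching Visit 6 if mapping were extended |
|---|---|---|---|
| 5% | 8.25 | 52.25 | 1.4 |
| 10% | 16.5 | 49.5 | 2.8 |
| 15% | 24.75 | 46.75 | 4.2 |
| 20% | 33 | 44 | 5.6 |

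The second column is an upper limit on lost ET data, because some leavers will have no ET assessment.

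**Step 4: illustration, all values assumed.** Let an abnormal finding occur in 2% of subjects who reach Visit 6 and 20% of leavers, all examined at ET.
- Arm losing 5%: 0.02 × 0.95 + 0.20 × 0.05 = 2.9%.
- Arm losing 20%: 0.02 × 0.80 + 0.20 × 0.20 = 5.6%.

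The Visit 6 row shows 2.0% in both arms, hiding a difference of 2.7 percentage points. If leavers have the same 2% rate, nothing is hidden; if their rate is lower, the Visit 6 row overstates. The size and direction depend on who leaves.

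**The case against.** **Other outputs show early leavers.** Protocol 9.1.4 defines the primary safety analysis as TEAEs, not the Visit 6 change tables. TEAEs cover the whole Safety Set through the end of the study, with severity, relatedness and action taken by arm (SAP 4.8.2). Reasons for study and treatment discontinuation are tabulated by arm (SAP 4.4). Ophthalmoscopy, comfort and laboratory listings cover the Safety Set. This stands. A reader might infer that the arm with more AE-driven withdrawal will appear safer overall; the documents do not support that, because such withdrawal would be visible in these outputs. Listings, however, give no by-arm summary, and a laboratory or cup-to-disc shift without symptoms may not be reported as an AE.

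**The reading relies partly on silence.** How the eCRF codes the ET visit is not shown. If ET were entered as Visit 6, or the tables carried an ET row, the values would be summarised. Nor are collected ET values missing data in the ordinary sense. This is fair and lowers certainty. But SAP 4.2.9 treats ET as distinct from scheduled visits, and the analysis rule should not be left to programming.

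**Comfort ratings may not exist.** The Visit 6 rating follows an observed in-clinic dose (Protocol 6.1.6), so subjects off treatment may have no ET rating. Early leavers also contribute a Visit 2 first-dose rating. Both points stand and make the gap smaller for comfort than for ophthalmoscopy and laboratory tests.

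**Other safety measures.** One might infer that IOP, BCVA, slit-lamp and hyperemia data are lost too. They are measured at every visit, so leavers appear in the summary of each visit attended. IOP and BCVA also have an any-visit count, which needs only a definition.

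**Conclusion.** The gap is real but narrow. Followed as written, the SAP gives by-arm change summaries of cup-to-disc ratio, drop comfort and laboratory values only for subjects who reach Visit 6, and leaves out ET values that sites are asked to collect. These tables could understate late safety or tolerability findings if withdrawal differs by arm.

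The number affected is unknown: at most about 8-33 of 165 under an assumed 5-20% early termination, and fewer where ET assessments were not done. The conclusion assumes that ET is stored as its own visit, as SAP 4.2.9 implies.

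A reader might locate the fault in the narrow scope of the 4.2.9 mapping. That is not the cause to correct: a wider mapping would send most ET visits to visits where these assessments are not scheduled. What is absent is a summary rule for ET values in SAP 4.8. The tables are descriptive, so no test or error rate is involved; the change is worth making because it serves the SAP's primary objective.

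**What to change.** In SAP 4.8.1 and 4.8.3:
- Keep the nominal Visit 6 row unchanged.
- Add a row for the last post-randomization value (Visit 6 or ET), with change from baseline (from Visit 1 for laboratory values), to Tables 14.3.6.x and 14.3.13.x.
- Add the same row to Table 14.3.11, restricted to subjects with an ET post-dose rating, and show their number.
- State that the any-visit counts in Tables 14.3.9.x and 14.3.10.x include ET and unscheduled readings.

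Leave the 4.2.9 mapping as it is for this purpose.

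**Cost.** SAP wording, an added row in six tables (2 + 3 + 1; one per parameter in the laboratory tables), and one definition covering four more. It uses data already requested and changes no study procedure. The downside is that the added row mixes different times on treatment, which is why it should stand beside the Visit 6 row and not replace it.
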